# 6.2.9 Samples for Biorepositories

Additional biological samples will be obtained to be stored to use in future studies of hemodialysis patients. In particular,  $\beta_2$ -microglobulin will be measured from samples obtained at baseline, 4 and 12 months. Patient consent will be obtained to specifically address the collection of these specimens. Among those participants who consent for storage of biological specimens, serum and plasma specimens will be shipped to the National Institute of Diabetes and Digestive and Kidney Diseases Biosample Repository at Fisher BioServices at study baseline, 4 months and 12 months. During the course of the trial, all studies using the biorepository samples must receive the approval of the FHN Ancillary Studies Committee and follow the study policies of the trial regarding ancillary studies.

# 6.3 Definitions, Monitoring and Reporting of Patient Events

# 6.3.1 Outcome Classification Committee

An Outcome Classification Committee will be composed of the Clinical Center Principal Investigators, who will review all deaths and 100 hospitalizations to verify cause of death or hospitalization (see below). The members of the Outcome Committee will be trained by the Data Coordinating Center in order to provide a standard classification system for patient deaths and hospitalizations. The Data Coordinating Center will remove any information that can identify the randomization status of the patient being reviewed so that members of the Outcome Committee will be blinded to the patient's treatment allocation.

# 6.3.2 Hospitalizations

All hospitalizations will be categorized by the Clinical Center (Site) PIs by access versus non-access hospitalization and by primary and secondary reason for hospitalization using one of a number of hospitalization categories by system, coded with a modification of the HEMO Study code list.

The detailed hospitalization discharge form will be completed by the Site PI, Co-Investigator or Collaborator from the patient's Clinical Center and reviewed by the Outcome Committee. After each hospitalization that does not lead to a death, a subject will sign a release to allow the hospital to provide the details of the hospitalization to the FHN Clinical Center team. (In addition, each subject will sign a blanket release form annually, to make it easier for the Clinical Centers to obtain details on hospitalizations that lead to death and to obtain details on deaths.) The Clinical Center will contact the hospital involved. Data to be obtained and recorded on the detailed hospitalization discharge form include date of admission, date of discharge, whether the patient was in the intensive care unit during the hospital stay, whether a vascular access procedure was performed during the hospital stay, the primary and secondary reason for hospitalization as coded by the categories on the form, and the standard adverse event questions about the expectedness and relatedness of the hospitalization. The answers to these questions will be based on either the discharge summary associated with that hospitalization or a narrative description of the hospitalization provided by a physician who was responsible for the care of the patient. The FHN detailed hospitalization discharge form will also capture whether the Site PI, Co-Investigator's or Collaborator's categorization was based on an actual discharge summary or some other form of documentation, and this form should be submitted to the Data Coordinating Center within 30 days of the patient's hospital discharge.

For the first 12 FHN Daily Study hospitalizations, the Outcome Committee will be available for consultation but will not do formal reviews. After the first 12 FHN Daily Study hospitalizations have occurred, for the next 52 daily study hospitalizations, the Clinical Center will send a hospitalization packet including the hospitalization discharge form and a discharge summary/narrative description to the DCC. The DCC staff will send create a hospitalization packet including these data and send this packet to one blinded member of the Outcome Committee, and he will complete Outcome Committee Hospitalization Review Form reassessing whether it was a CV or Access hospitalization. (The precise "reason for hospitalization" code associated with the hospitalization is not reassessed.) If the CV and access determination coded by the Outcome Committee member and the Clinical Center PI, Co-Investigator or Collaborator differ, then the case will be adjudicated by the Outcome Committee during the monthly conference call until resolution can be reached. The final categorization with respect to CV and Access will be recorded in the "final categorization" section at the end of the Outcome Committee Hospitalization Review Form. The hospitalization code chosen by the committee as the "final categorization" will be used for subsequent analyses of these 52 hospitalizations.

The agreement of the Outcome Committee and Clinical Center classifications of the initial 52 hospitalizations will be evaluated as part of the Vanguard assessment of the trial. Subsequently, 12 hospitalizations per year (one hospital admission form per calendar month) will be selected for review by a member of the Outcome Committee and adjudication by the Outcome Review Committee if necessary.

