#### 6.3.3 Deaths

The death form will be completed by the Principal Investigator from the involved Clinical Center, who will classify the death using a modification of the HEMO Study coding system. This system will allow for the classification of deaths by organ system, such as cardiac and infection-related. A death packet with the death form and specific patient information will be sent by the Clinical Center to the Data Coordinating Center, who in turn will forward this data to members of the Outcome

Committee. For hospitalizations resulting in death, the same information as described above for hospitalizations will be obtained. If the death did not occur in the hospital, then the principal investigator will provide a narrative describing the circumstances of the patient's death and the presumed cause of death based on the patient's history and events leading up to the patient death. One member of the Outcome Committee will review this information and verify the cause of death on the death form. If the death coded by the Outcome Committee member and the Clinical Center PI differ, then the case will be discussed by the Outcome Committee during the monthly conference call. The death code chosen by the committee will be used for subsequent analysis.

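### The Outcome Committee reviewer is blinded to treatment arm but not to the site's own coding, so the second reading of access and cardiovascular admissions is not independent

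*Protocol*

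**What the plan says.** Section 6.3.2 gives the first classification to the site: "All hospitalizations will be categorized by the Clinical Center (Site) PIs by access versus non-access hospitalization". The form is a site document too: "The detailed hospitalization discharge form will be completed by the Site PI, Co-Investigator or Collaborator from the patient's Clinical Center". Its contents include "the primary and secondary reason for hospitalization as coded by the categories on the form", and whether a vascular access procedure was done during the stay.

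The first 12 admissions have no formal review. For the next 52, "the Clinical Center will send a hospitalization packet including the hospitalization discharge form and a discharge summary/narrative description to the DCC". The coordinating center is then to "create a hospitalization packet including these data and send this packet to one blinded member of the Outcome Committee". That member decides again on the cardiovascular and access labels only; the detailed reason code is left as it is. Differences go to the committee's monthly call, and the committee's final category is used in the analysis of these 52 admissions.

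On masking, Section 6.3.1 says: "The Data Coordinating Center will remove any information that can identify the randomization status of the patient being reviewed". Neither section says that the site's codes are hidden from the reviewer.

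Section 6.3.2 also plans a check: "The agreement of the Outcome Committee and Clinical Center classifications of the initial 52 hospitalizations will be evaluated as part of the Vanguard assessment". Afterwards one admission a month is reviewed. Section 6.3.1 puts the number of reviewed hospitalizations at 100.

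For deaths, Section 6.3.3 says: "One member of the Outcome Committee will review this information and verify the cause of death on the death form".

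**The concern.** A second classification tells us most about the first when it is made without knowledge of it. Here the reviewer opens a packet that already holds the site's answer. A reader in that position tends to confirm it, above all in borderline cases.

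The access label decides which admissions count in the rate of non-access hospitalization or death, a main secondary outcome (Sections 5.1.3.7 and 9.6). Site staff know the arm (Section 2.2), and Section 3.3 itself names staff enthusiasm for daily dialysis as a risk of bias. Section 5.1.3.7 regards the evidence of benefit as stronger for non-access than for access admissions, and expects that access admissions will be hard to identify completely. Unclear cases, and an expectation that could colour how they are labelled, are thus both on record.

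At stake are the labels of the reviewed admissions, which the committee reading is meant to correct, and the agreement figure, which will be read as evidence about the quality of site coding.

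**Working it through.** The protocol states no agreement target, kappa or power for this check, so there is no figure to reproduce. The first step is a reading of the text; the second is an illustration that rests on assumptions.

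**Step 1: what the reviewer sees.**
- Written by the site: the discharge form with primary and secondary reason codes and the access-procedure item (6.3.2).
- Sent to the reviewer: a packet that includes that form and the discharge summary or narrative (6.3.2).
- Removed first: information on randomization status (6.3.1).
- Therefore visible: the site's reason codes. A separate access or cardiovascular tick-box is not among the listed items, but the label can largely be inferred from the codes.

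**Step 2: how far this could move the agreement figure.** Let *d* be the share of admissions on which an independent reader would differ from the site, and *a* the probability that a reader who sees the site's code defers to it in such a case. Neither value is in the documents. With *n* = 52:

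- expected agreement = 1 − *d*(1 − *a*)
- expected disagreements = 52 × *d*(1 − *a*)

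| *d* | codes hidden (*a* = 0) | *a* = 0.5 | *a* = 0.75 |
|---|---|---|---|
| 0.10 | 90%; 5.2 | 95%; 2.6 | 97.5%; 1.3 |
| 0.20 | 80%; 10.4 | 90%; 5.2 | 95%; 2.6 |
| 0.30 | 70%; 15.6 | 85%; 7.8 | 92.5%; 3.9 |

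For example, 1 − 0.20 × (1 − 0.5) = 0.90, and 52 × 0.20 × 0.5 = 5.2. Any *a* above zero raises the agreement. At *d* = 0.20 and *a* = 0.75 the chance of at least one disagreement is still 0.93; it is zero only at *a* = 1.

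**Step 3: disagreement that differs by arm.** Suppose the 52 split evenly, 26 per arm, with independent disagreement of 30% in one arm and 10% in the other. A two-sided 5% comparison of proportions has power 0.44 with codes hidden, 0.22 at *a* = 0.5 and 0.13 at *a* = 0.75. The check is weak for this purpose even without anchoring, and weaker with it.

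**Step 4: how many labels the review touches.** Section 9.11 gives 1.19 non-access hospitalizations per year. With 250 patients, no treatment effect and an assumed 0.85 to 1.0 patient-years each:

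- 1.19 × 250 × 0.85 = 253
- 1.19 × 250 × 1.0 = 298

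Even the stated 100 reviews would be 100/298 = 34% to 100/253 = 40% of that number, and the share of all admissions is smaller because access admissions come on top. Most labels stay as the site set them.

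**The case against.** The best defence is that the committee's stated task is to verify site coding against source documents, which is a coherent design. The reviewer is blinded to arm, has the summary or narrative, completes a separate review form and may differ from the site, and differences are adjudicated. That stands, and it limits what can be concluded.

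- A reader might infer that the check cannot detect biased site labels. The documents do not support this: Step 2 shows that disagreements disappear only if the reviewer always copies the site.
- A reader might infer that a false pass at the Vanguard review lets the trial relax its checking. There is no such gate. The Vanguard benchmarks in Section 4 are recruitment and attendance, no threshold is set for agreement, and the later drop to 12 reviews a year is not conditional on it.
- A reader might go on to attach an inflated type I error for the main secondary outcome to this flaw. That would price site relabelling across the whole trial. Most admissions are never reviewed, so masking would not change their labels. Nor would masking reliably expose a modest shift. If 75% of about 26 daily-arm admissions were non-access (an assumption) and 10% of those were moved, that is 26 × 0.75 × 0.10 = about 2 cases, against 5.2 to 10.4 background disagreements at *d* = 0.10 to 0.20. Section 6.3.2 also does not say that agreement will be compared by arm.
- Other outcomes give some protection. Section 5.1.3.7 also lists all hospitalizations or death, which does not use the access label, and access hospitalizations, which would rise if admissions were moved there. Section 9.4 reads isolated nominally significant secondary results as consistent with type I error.
- For deaths, the cause code enters neither the co-primary composites, which rank by survival time (9.3), nor the non-access hospitalization or death outcome (9.6).

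What the defence does not answer is that the second reading is made with the first one in view.

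**Conclusion.** The point holds in a limited form. Sections 6.3.1 and 6.3.2 blind the reviewer to arm but not to the site's coding. The committee's reading is therefore not independent of the unblinded site's reading, the agreement on the 52 admissions is likely too high, and the review is less able to correct or reveal mislabelling of access versus non-access admissions.

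That agreement is too high is an inference about how readers behave. Its size cannot be derived from the documents, and the table above only shows a range under assumed values of *d* and *a*. The direct effect on the analysis is confined to the reviewed admissions. No type I error figure should be attached to this point. It is a cheap improvement to a stated procedure, not an error that undermines the outcome.

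**What to change.** In Section 6.3.2, state that the coordinating center withholds the site's reason codes and any access or cardiovascular category, along with arm information, until the reviewer has recorded both labels on the review form from the discharge summary or narrative alone. The coordinating center then compares the two classifications and sends differences to the existing monthly call. The same rule should cover the later monthly reviews.

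The cost is a little more masking at the coordinating center, which already redacts packets, and possibly more cases on the call. No reviewers or reviews are added. Masking the site's cause-of-death code in Section 6.3.3 in the same way is optional, because the co-primary outcomes and the non-access hospitalization or death outcome do not use that code.

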#### 6.3.3 Deaths

The death form will be completed by the Principal Investigator from the involved Clinical Center, who will classify the death using a modification of the HEMO Study coding system. This system will allow for the classification of deaths by organ system, such as cardiac and infection-related. A death packet with the death form and specific patient information will be sent by the Clinical Center to the Data Coordinating Center, who in turn will forward this data to members of the Outcome

Committee. For hospitalizations resulting in death, the same information as described above for hospitalizations will be obtained. If the death did not occur in the hospital, then the principal investigator will provide a narrative describing the circumstances of the patient's death and the presumed cause of death based on the patient's history and events leading up to the patient death. One member of the Outcome Committee will review this information and verify the cause of death on the death form. If the death coded by the Outcome Committee member and the Clinical Center PI differ, then the case will be discussed by the Outcome Committee during the monthly conference call. The death code chosen by the committee will be used for subsequent analysis.

## 6.3.4 Vascular Access Complications

All vascular accesses will be tracked for complications using a modification of the Dialysis Access Consortium Study vascular access forms. A form will be completed on each patient at the time of randomization that will classify the type and location of the vascular access in use at that time. A vascular access complication form will be completed whenever the study patient undergoes one or more of the following vascular access procedures: access failure (thrombosis or removal requiring placement of a new access), placement of a new vascular access, access intervention (angioplasty, stenting, surgical revision, fibrin sheath stripping, etc., but not TPA instillation or venogram only). The procedures performed for these access complications will also be noted on this form. Vascular access infections not requiring removal of the access will not be recorded. Information on vascular access complications will be provided to the DSMB to monitor the rates of access complications in each arm of the study.

## 6.3.5 Withdrawal from Study Protocol

All withdrawals from the study protocol will be tracked and the reason for withdrawal will be ascertained (see Sections 7.3 and 7.4).

### 7. Deviations from Trial Protocol, Action Items and Stop Points

### 7.1 Nonadherence

All subjects will be strongly encouraged throughout the study to adhere to the randomized therapy. However, for subjects in the daily HD group who are not able to adhere to the 6 times per week schedule as prescribed, a series of alternative prescription options will be offered by the Kinetic Modeling Committee (see Section 3.1.6), including a temporary "holiday" from the randomized therapy. Patients will continue to be followed for all data collection, irrespective of their adherence to the randomized therapy (intent to treat analysis).

### 7.2 Action Items

# 7.2 Action Items

The DCC will report and the Outcome Committee will review (in conjunction with Kinetic Modeling Committee) any patient who has persistent underdialysis (i.e., for conventional group, not meeting eKt/V of 1.10 per session for 2 or 3 consecutive measurements; for daily and nocturnal group, not meeting a std Kt/V of 2.0 for 3 consecutive measurements)

a) DCC will report and the Recruitment and Adherence Committee will review any patient who has persistent nonadherence to therapy. Persistent nonadherence to be defined and monitored with appropriate action by adherence committee (in conjunction with Kinetic Modeling Committee).

- b) DCC will report and the Standards of Care/Clinical Management Committee will review any patient who has persistent hypophosphatemia (serum phosphate level less than the lower limit of the normal range) on 2 or 3 consecutive monthly measurements
- c) The Central HRQL Survey Center will report within 24 hours to the research coordinator or treating nephrologist any patient who has potentially life-threatening findings on tests done exclusively for the purpose of the study. These findings will also be reported to the DCC who will report these findings in a timely manner to the study center when received by the database. These findings may include, but are not limited to:
  - i) scores above a certain threshold that indicates depression on the Beck Depression Inventory
  - ii) answers 2 or 3 on question #9 of the Beck Depression Inventory ("would you kill yourself")
- d) The Central Holter Core will transmit a report to the Data Coordinating Center for any patient who has potentially clinically relevant findings on tests done exclusively for the purpose of the study. The DCC will report these findings in a timely manner to the study center when received by the database. These findings may include, but are not limited to: arrhythmias due to ventricular tachycardias, torsades de pointes, AV blocks 2b and 3, sinus arrest / SA blocks 3, and atrial fibrillation.
- e) The Central Cardiac MRI Core will transmit a report to the Data Coordinating Center for any patient who has potentially clinically relevant findings on tests done exclusively for the purpose of the study. The DCC will report these findings in a timely manner (approximately 2-3 weeks from MRI Core Physician review) to the study center when received by the database. These findings usually include clinically relevant abnormalities noted during the performance of the cardiac MRI. These will relate to abnormalities noted in the pericardium, myocardium, valvular structures and/or contiguous vascular structures. Clinically relevant abnormalities will be adjudicated based on the best clinical judgment of the reviewing physician at the Central Cardiac MRI Core.

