# 6.2.6 Heart Rate Variability/Holter Monitoring

Heart rate variability will be measured at baseline and at the F12 visit using 24-hour Holter measurements from KCI (Table 11 C). Holter at baseline is not required for randomization.

It is recommended, if possible, for Holter monitoring to be done on the first dialysis day following the weekend. Each 24-hour Holter analysis period will commence immediately after placement of the Holter equipment, which will take place at any point in time in the hour proceeding the start of dialysis.

Analysis will be carried out for three periods:

Period 1: the time between placement of the Holter and the end of the dialysis session,

Period 2: the time between the end of the dialysis session and starting time + 12 hours,

Period 3: the time between the end of Period 2 and starting time + 24 hours.

Each study site will download the data onto CD and send to the core lab, where data will be analyzed by a trained person blinded to the patient's treatment allocation.

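### Section 7.2 gives potentially life-threatening questionnaire findings a direct 24-hour report, but has no urgent route for Holter or cardiac MRI findings

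*Protocol*

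**What the plan says.** Three items in Protocol Section 7.2 deal with findings on tests done only because the patient is in the study.

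- **Item (c), questionnaires.** "The Central HRQL Survey Center will report within 24 hours to the research coordinator or treating nephrologist any patient who has potentially life-threatening findings". The DCC route is additional: "These findings will also be reported to the DCC who will report these findings in a timely manner to the study center". The examples are depression scores above a threshold and certain answers to the suicide question of the Beck Depression Inventory.
- **Item (d), Holter.** "The Central Holter Core will transmit a report to the Data Coordinating Center for any patient who has potentially clinically relevant findings". The site hears from the DCC: "The DCC will report these findings in a timely manner to the study center when received by the database". The findings may include "arrhythmias due to ventricular tachycardias, torsades de pointes, AV blocks 2b and 3, sinus arrest / SA blocks 3, and atrial fibrillation".
- **Item (e), cardiac MRI.** "The Central Cardiac MRI Core will transmit a report to the Data Coordinating Center", and then "The DCC will report these findings in a timely manner (approximately 2-3 weeks from MRI Core Physician review) to the study center". Clinical relevance is decided by the reviewing physician at the MRI Core.

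Sections 6.2.5 and 6.2.6 describe central reading of both tests. For the Holter, "Each study site will download the data onto CD and send to the core lab".

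**The concern.** Item (c) has two routes: a direct report with a deadline for what may threaten life, and a DCC report besides. Items (d) and (e) have only the second. Yet the Holter list includes rhythms that can be life-threatening and places them in one tier with atrial fibrillation. The MRI item gives a lag in weeks that starts only after a physician has reviewed the scan, and allows no exception.

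What is at stake is participant safety. If staff follow the items as written, urgent information that a study reader already has reaches the treating team late, although the same list provides a quick route for another kind of urgent finding. No estimate, test or error rate in the trial depends on this.

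**Working it through.** No sample size, power or error-rate calculation applies. The check sets the three items side by side.

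| | (c) Questionnaires | (d) Holter | (e) MRI |
|---|---|---|---|
| Trigger | potentially life-threatening | potentially clinically relevant | potentially clinically relevant |
| Sender reports to | coordinator or treating nephrologist, and also the DCC | DCC | DCC |
| Deadline to site | 24 hours (direct report) | none in figures | about 2-3 weeks |
| Clock starts at | not stated | receipt by the database (no figure) | MRI Core physician review |
| Urgent tier | yes | none | none |

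**Step 1: the stated intervals.** For MRI, 2 × 7 = 14 days and 3 × 7 = 21 days, or 14 × 24 = 336 hours and 21 × 24 = 504 hours. Against 24 hours, the ratios are 336/24 = 14 and 504/24 = 21. The time from scan to physician review comes on top, and Section 7.2 sets no limit on it.

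**Step 2: Holter.** Item (d) gives no number, so no interval can be computed. The time to send the CD to the core and have it read comes first and is also not limited.

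**Step 3: do the triggers explain the difference?** Only in part. A longer route for merely clinically relevant findings can coexist with a 24-hour route for life-threatening ones. But the list in (d) contains findings that can meet the higher trigger, and (d) does not separate them. Item (e) covers any abnormality of the pericardium, myocardium, valves or adjoining vessels that the reviewing physician finds clinically relevant, again without separating the urgent ones.

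**Step 4: is a faster route written elsewhere?** Sections 6.2.5 and 6.2.6 describe acquisition and central reading and give no urgent contact. Section 10.2 covers adverse-event and safety reports to committees and to the monitoring board, not core findings to sites. Section 7.2 does not refer to the Manual of Operations for these items.

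**The case against.** The strongest reply is that the comparison is not like with like. The 24-hour rule is for life-threatening findings, while (d) and (e) use a lower trigger, and different timing for different triggers is no contradiction. There is also a plausible practical reason, although the protocol does not state it. A telephone interview can reveal suicidal intent as it happens, whereas a Holter event is past by the time the recording has been sent and read. This much stands: the 24-hour rule does not cover every questionnaire result, and a deadline that starts at core reading does not shorten shipping or reading. It does not explain why the items lack a tier for findings that do meet the higher trigger.

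A second reply is that the protocol leaves operational detail to a Manual of Operations elsewhere, and that nothing forbids a core from telephoning a site. This also stands as a limit on the point. However, item (e) is not silent on timing; it gives a figure in weeks.

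A reader might infer more than the text supports:

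- **That arrhythmias wait 2-3 weeks.** That figure belongs to MRI alone. For Holter the time is not quantified.
- **That findings are withheld, or that no clinician outside the study sees the tests.** The items set out a route and do not prohibit others. Being done only for the study explains why a test is performed, not who may look at it. Local review is neither described nor excluded.
- **That patients could be wrongly randomized because a baseline Holter is not required.** Arrhythmia is not listed as an exclusion criterion in Section 2.5.2, and faster reporting after core reading would not make the baseline Holter compulsory.
- **That the number of scans and recordings measures the problem.** The rules act on recordings with relevant findings, and the protocol gives no rate for these. Baseline Holter is optional, and Section 9.11 assumes that 12-month LV mass is obtained in only 80% of patients.

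**Conclusion.** The point holds as an inconsistency within one list. Item (c) has a direct, timed route for potentially life-threatening findings. Item (d) names findings that can be of that kind and has neither an urgent tier nor a time limit. Item (e) states an interval 14 to 21 times as long as that in (c), with no urgent exception.

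How many patients would be affected cannot be estimated from the protocol. The conclusion assumes that staff follow Section 7.2 as written and that no document outside the protocol supplies an expedited route. If the manual has one, a cross-reference in Section 7.2 settles the matter. The change should be made on safety grounds; it has no bearing on the validity of the analysis.

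**What to change.** Reconcile items (d) and (e) with item (c) by adding an urgent tier to each:

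- When the core reader judges a Holter or MRI finding potentially life-threatening, the core notifies the research coordinator or treating nephrologist directly, by the route and within the time already written in (c), and copies the DCC.
- All other clinically relevant findings stay on the existing DCC route.
- The clinical response stays with the treating physician; the protocol need only say who is told and when.

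If such a route already exists in the Manual of Operations, cite it in Section 7.2 and make the time stated in (e) consistent with it.

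The cost is wording in the protocol and core manuals, plus one direct message per urgent finding from readers who already write a report. No extra reader or procedure is needed. The small downside is that the cores must hold site contact details, and the contact must not reveal treatment allocation to readers who are blinded to it.
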